- CT and MRI scans if clinically indicated can be performed with or without intravenous contrast as per institutional guidelines at screening, C8D1, C13D1 and C17D28 (a window of ± 7 days for all scans is allowed). DEXA scan will be performed at screening and after completion of 1 year of treatment. CT or Brain MRI: Brain imaging studies are not required for eligibility if the subject has no neurologic signs or symptoms suggestive of brain metastasis. Subjects

with neurological symptoms are recommended to undergo a head CT scan (with or without intravenous contrast) or brain MRI (with or without intravenous contrast) to exclude brain metastasis. If brain imaging studies are performed, they must be negative for CNS disease. Skull bone involvement without neurological impact by prostate cancer is allowed. A bone scan will be performed at baseline, C8D1 and after completion of 1 year of treatment.

9. All subjects will receive androgen deprivation therapy with a LHRH agonist (any LHRH agonist such as leuprolide acetate or goserelin acetate is acceptable) or a LHRH antagonist (degarelix) or bilateral orchiectomy per the treating physician. Androgen Deprivation therapy with LHRH agonist or LHRH antagonist will be given continuously.
10. MANDATORY: Serum submission for Bone Turnover Markers: Pre-Dose Cycle 1 Day 1 (late induction group) and thereafter on Day 1 of each cycle during the remaining 6 months of protocol specified therapy and at End of Treatment (both induction groups). CTCs: For following time points only: C1D1 (late induction group only); C2D1 (early induction group only); C4D1; EOT visit. CTCs will be collected for all subjects (n = 204). See Correlative Laboratory Manual (CLM) for collection, labeling and shipping instructions.
11. MANDATORY: Whole blood for banking is to be collected pre dose Cycle 1 Day 1 (late induction group) or pre dose Cycle 2 Day 1 (early induction group) and at EOT. Serum and plasma are to be collected at Pre-Treatment Cycle 1 Day 1 (late induction group) or Cycle 2 Day 1 (early induction group) and at EOT. See CLM for collection, labeling, processing and shipping instructions.

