### 7.7 Maintenance: Cycle 13 Day 1; 12 months from ADT initiation ( $\pm 7$ days):

- Clinical: Physical examination including BP measurement, weight, ECOG performance status, assessment of adverse events and concomitant medications. Close monitoring for fractures should be done during all physical exams. If a fracture is suspected radiological exams should be performed per clinical guidelines. Subjects should be encouraged to contact the site investigator for any new onset pain or increase in pain in sites of known bone disease.
- Laboratory Testing:
  - CMP to include sodium, potassium, chloride, bicarbonate, blood urea nitrogen (BUN), serum creatinine, glucose, calcium, total protein, albumin, AST, ALT, alkaline phosphatase, total bilirubin, magnesium, phosphorus
  - CBC (WBC with differential and platelet count, hemoglobin and hematocrit)
  - Serum testosterone
  - Alkaline phosphatase
  - PSA
- Imaging:
  - CT or MRI abdomen/pelvis
  - DEXA scan
  - Bone Scan
  - Chest x-ray or Chest CT if clinically indicated

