### 7.10 End of Treatment (EOT) and Follow Up

The end of treatment/follow up column will be utilized for subjects that come off protocol therapy (radium-223 dichloride if randomized to that Arm and ADT) for toxicity or progression. If this occurs, subjects should have an end of treatment visit 30 days ( $\pm$  7 days) after discontinuation of protocol therapy. Subjects will then continue to be followed every 3 months for a total of 2 years from the date of randomization. Follow up may occur via phone call, email or other communication. If available by medical record review, alk phos, PSA, AE/concomitant medication should be obtained. Testing to be done at the EOT visit:

- Circulating tumor cell's (CTCs)
- Serum bone turnover markers
- Banking Samples: serum, plasma
- Alkaline phosphatase
- PSA

If a subject withdraws consent, he is deemed **“off study”**. “Off study” subjects will not be followed further.

A subject will be discontinued from the protocol specified therapy under the following circumstances:

- If there is evidence of radiologic disease progression or symptomatic deterioration despite castration range serum testosterone level ( $< 50$  ng/dL). Such subjects can go on to other treatment outside the study as clinically indicated including continuation or initiation of radium-223 dichloride therapy. They will remain on follow-up portion of the study for a total of 2 years from the date of randomization.
- If there is development of castration-resistant prostate cancer by PSA criteria in conjunction with castration range serum testosterone level ( $< 50$  ng/dL). Castration resistant prostate cancer is defined as two consecutive increases in PSA over the nadir PSA, at least two weeks apart **AND** an absolute increase of at least 2 ng/mL from the nadir PSA (or from baseline PSA if there was no drop in PSA after starting treatment). Discontinuation of bicalutamide may be attempted at the investigator's discretion in such cases and would NOT constitute going “off treatment”. If no response to bicalutamide discontinuation, such subjects may receive other treatment outside the study as clinically indicated including continuation or initiation of radium-223 dichloride therapy. They will remain on follow-up portion of the study for a total of 2 years from the date of randomization.

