## 8.2 Progression Criteria

**8.2.1 PSA progression** is defined by two consecutive increases in PSA over the nadir PSA, at least two weeks apart AND an absolute increase of at least 2 ng/mL from the nadir PSA (or from baseline PSA if there was no drop in PSA after starting treatment).

**8.2.2 Radiographic Skeletal progression on bone scan** is defined as 2 or more new lesions on radionuclide bone scans (PCWG2 criteria). Should two or more new bone lesions be evident at the first imaging assessment (at end of protocol specified therapy), two or more additional new lesions must be evident on a confirmatory assessment at least 6 weeks later.

A bone scan may be ordered at the discretion of the treating physician within the first 7 months of protocol treatment for symptoms e.g. bone pain. If new bone lesions appear in the absence of a rising PSA within the first 7 months of protocol treatment, the site investigator at the institution must consult the sponsor-investigator (via the HCRN Project Manager) to discuss the possibility of tumor flare.

For bone disease documented on bone scan only, increased uptake does not constitute unequivocal progression. However, increase in the soft tissue component of a lesion as measured by CT or MRI would constitute progression.

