### 12.6 Analysis of Primary Objective

Subjects will be assessed for radiographic progression as described in section 8. Time from first dose of ADT to radiographic progression or death, whichever occurs first, will be calculated for each subject. For subjects who discontinue study treatment due to reasons other than death or investigator assessed progression, every effort will be made to continue tumor assessments on schedule until radiographic progressive disease or subject death. Subjects who do not have radiographic progression or death will be censored at their last measure for radiographic progression. The primary hypothesis test will be conducted at a one-sided 0.1 significance level using a stratified log-rank test. Kaplan-Meier methods will be used to report rPFS graphically by arm including the median rPFS and 12 and 24 month rPFS proportions in the ITT population. The log-rank test without stratification will be used as a sensitivity analysis.

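### A bone finding at the first scan (C8D1) needs confirmation to count for rPFS, but no confirmatory scan is scheduled before C13D1 and a switch is allowed sooner, so the case can be censored at C8D1

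*Combined protocol and SAP*

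**What the plan says.** **Definition.** Section 8.2.2 takes two or more new lesions on bone scan as skeletal progression, with an exception for the first scan. If such lesions are "evident at the first imaging assessment (at end of protocol specified therapy), two or more additional new lesions must be evident" on a further assessment no sooner than 6 weeks later. It names no visit for that assessment.

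**Calendar.** Footnote 8 of the Section 7 calendar reads: "A bone scan will be performed at baseline, C8D1 and after completion of 1 year of treatment". The one-year scan is in Section 7.7 ("Maintenance: Cycle 13 Day 1; 12 months from ADT initiation"). Section 7.9 (C17D28) has CT or MRI but no bone scan.

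**Stopping and switching.** Section 7.10 ends protocol therapy as follows: "If there is evidence of radiologic disease progression or symptomatic deterioration despite castration range serum testosterone level". The word confirmed does not appear. It goes on: "Such subjects can go on to other treatment outside the study as clinically indicated including continuation or initiation of radium-223 dichloride therapy". Of later contact it says: "Follow up may occur via phone call, email or other communication". The end-of-treatment tests it lists include no imaging.

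**Analysis.** Section 12.6 brings in the definition: "Subjects will be assessed for radiographic progression as described in section 8". It promises every effort to keep scanning until progression or death, but limits that promise: "For subjects who discontinue study treatment due to reasons other than death or investigator assessed progression". Sections 8.8 and 12.6 censor men without progression or death at their last radiographic assessment.

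**The concern.** Take a man with two new bone lesions at C8D1 and no soft-tissue progression. His site may regard this as progression, stop protocol therapy and start something else. The analysis does not yet regard it as progression. If nobody rescans him and he is alive, he leaves the primary analysis as censored at C8D1.

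Whether a possible primary event is counted or censored then depends on an open-label decision prompted by the same scan. Such censoring is informative, because the men removed are those most likely to have progressed. A confirmatory scan that was never done cannot be recovered at analysis.

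**Working it through.** **1. The plan's own figures.** Section 12.1 gives one-sided alpha 0.10, 90% power, HR 0.632, 1:2 allocation (68 and 136), medians of 12 and 19 months, 10% yearly dropout, 24 months of accrual and a 48-month study.

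- Events: (1.2816 + 1.2816)² / [(1/3)(2/3)(ln 0.632)²] = 6.570 / (0.2222 × 0.2106) = 140.4. The plan says 140.
- Expected events from 204 men, with exponential times and dropout hazard −ln(0.9)/12 per month: 53.1 control + 87.1 radium = 140.1.

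Both figures reproduce.

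**2. Timing.** Cycles are 28 days.

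- C8D1 is day 7 × 28 = 196 (196/30.4375 = 6.44 months).
- C13D1 is day 12 × 28 = 336 (11.04 months).
- The gap is 140 days, or 20 weeks (18 to 22 with ±7 days at each visit). Confirmation is valid from week 6, so an unscheduled scan could serve in the 14 weeks before C13D1.

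**3. How many men could be affected.** Under the plan's medians, events by C8D1 are:

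- control: 68 × (1 − 2^(−6.44/12)) = 68 × 0.311 = 21.1
- radium: 136 × (1 − 2^(−6.44/19)) = 136 × 0.209 = 28.5
- total: 49.6

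This total includes deaths and soft-tissue progression, which need no confirmation. The documents give no bone-only share and no loss rate. I assume a 50% share (24.8 men) and vary the loss.

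**4. Effect on the test.** I simulated the plan's design with an unstratified log-rank test. Each lost man was censored at 6.44 months. The null has a 12-month median in both arms. Ranges cover separate runs of 6,000 to 25,000 trials (Monte Carlo standard error about 0.002 to 0.004).

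| Loss of bone-only early events (control / radium) | Events | Power | Null rejection |
|---|---|---|---|
| none | 140 | 0.91 | 0.10 to 0.11 |
| 10% / 10% | 138 | 0.90 to 0.91 | 0.11 |
| 25% / 25% | 134 | 0.89 to 0.90 | 0.10 to 0.11 |
| 50% / 50% | 128 | 0.87 to 0.89 | 0.10 |
| 15% / 10% | 137 | 0.89 | 0.09 to 0.10 |
| 50% / 25% | 131 to 132 | 0.81 to 0.82 | 0.05 to 0.06 |
| 10% / 15% | 137 | 0.91 | 0.12 |

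The closed form agrees for equal loss: Φ(√(128 × 2/9) × 0.4589 − 1.2816) = 0.878, against 0.899 at 140 events. With a 75% bone-only share and 50% equal loss, 122 events remain and power is about 0.87. Equal loss mainly lengthens the medians: at a 50% share and 50% loss, control goes from 12.0 to 13.9 months and radium from 19.0 to 20.7. The hazard ratio stays at 0.63 to 0.64.

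Every lost case is treated here as a true progression whose later death is not counted. Some would be flare, and some deaths would be counted, so the losses shown lean high.

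**The case against.** The strongest reply is that the sections, read together, already settle the matter. Section 12.6 uses the Section 8 definition, so an unconfirmed first-scan finding is not progression, and 12.6 then asks for scans to continue. On that strict reading nothing conflicts. This stands as an interpretation. But 7.10 is the rule a site follows when it stops therapy. It does not say that progression must be confirmed, and 12.6 exempts what the investigator assessed, without saying whether an unconfirmed C8D1 finding counts as that.

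A reader might infer that only C13D1 can supply the confirmation. The documents do not support that. Section 8.2.2 names no visit, and any scan from week 6 would qualify. C13D1 is only the one such scan on the calendar.

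The route is also narrow. Soft-tissue progression, growth of the soft-tissue component of a bone lesion, and death all count without a confirmatory bone scan. Section 8.2.2 requires a consultation with the sponsor-investigator about flare for new bone lesions without a rising PSA in the first 7 months. C8D1 falls in that period, but the consultation covers only those men and does not order a rescan. Sections 8.2.4 and 8.14 ask for efforts to document progression after stopping, but only for symptomatic deterioration.

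Finally, equating the first scan with C8D1 is an inference from the calendar. Section 8.2.2 allows an earlier scan for symptoms. If that scan came first, C8D1 could itself be the confirming one.

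**Conclusion.** The concern holds as a misalignment between the stopping rule and the analysis rule for the primary endpoint. It affects bone-only C8D1 findings in men who are switched, not rescanned and alive. Its size and direction are unknown, because the bone-only share and all loss rates above are assumptions. Equal loss of up to half of the assumed bone-only early events costs about 2 to 4 points of power.

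A reader might infer that the treatment comparison is biased or the type I error inflated. The documents do not establish either. The one asymmetry they suggest is that control men may start radium-223 off study. That would mean more loss in control, which is conservative: null rejection falls below 0.10 and power is lost. Inflation would need more loss in the radium arm, and the documents give no reason to expect that.

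This is a cheap improvement that has to be made prospectively. It is not a flaw that undermines the design.

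**What to change.** - (a) Add a calendar footnote requiring the 8.2.2 confirmatory bone scan at least 6 weeks after C8D1 for any man with two or more new lesions there. It should apply in both arms, on or off therapy, and before new therapy where possible.
- (b) State in 7.10 and 12.6 that first-scan bone progression means progression confirmed under 8.2.2, and that tumor assessments continue until then.
- (c) Add a sensitivity analysis that counts unconfirmed C8D1 bone progression followed by new anticancer therapy as an event at C8D1, and report the number of such men by arm.

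Optionally, for consistency, apply to rPFS the rule in 8.6 that dates bone progression at the first scan. Sections 8.7 and 8.8 give no such rule. Dating all bone-only early events at C13D1 instead leaves power at 0.90 to 0.91.

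The cost is low: some wording, one footnote and one analysis. Sites must track one conditional scan in men off therapy, which 8.2.2 already implies. The sensitivity analysis may count some flare as progression and itself depends on the switch decision, so it supplements the primary analysis and cannot replace it.

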## 3 ELIGIBILITY CRITERIA

### 3.1 Inclusion Criteria

#### Definitions:

- **Androgen Deprivation Therapy** includes LHRH agonist or LHRH antagonist or bilateral orchiectomy. Anti-androgen receptor blockers (e.g. bicalutamide) do not constitute androgen deprivation therapy.
- **Protocol specified therapy** refers to the androgen deprivation therapy (see above) with or without radium-223 dichloride.

1. All subjects or their legally authorized representative must be informed of the investigational nature of the study and provide written informed consent and HIPAA authorization for release of personal health information before performance of any study related procedure not part of routine medical care.  
**NOTE:** HIPAA authorization may be included in the informed consent or obtained separately.
2. Men  $\geq$  18 years of age at the time of informed consent.
3. Histological or cytological evidence of prostate adenocarcinoma.
4. All subjects must have radiologic or pathologic evidence of skeletal metastases with  $\geq$  2 skeletal lesions with or without pain at baseline on bone scan or axial imaging or with 1 skeletal lesion and bone pain within 28 days prior to the registration.
5. All subjects must have a radiographic assessment (chest or abdominal/pelvic CT or MRI) within 28 days prior to registration but do not need to have measurable disease.
6. ECOG (Eastern Cooperative Oncology Group) Performance Status of 0-2 within 28 days prior to registration (see Study Procedures Manual [SPM] for ECOG Performance Status definitions). ECOG Performance Status of 3 will only be allowed if judged by the site investigator as attributable exclusively to bone pain.
7. Subjects must fall into one of the two populations below:
  - **Early Induction Group:** Subjects who have started androgen deprivation therapy (luteinizing hormone–releasing hormone (LHRH) agonist or antagonist therapy with or without an antiandrogen agent) a maximum of 28 days before registration and who otherwise meet all the eligibility criteria.
  - **Late Induction Group:** Subjects who have NOT started any androgen deprivation therapy (luteinizing hormone–releasing hormone (LHRH) agonist or antagonist therapy with or without an antiandrogen agent).

8. Anti-androgen receptor antagonist therapy must be bicalutamide. Subjects already started on other anti-androgens must be willing to switch over to bicalutamide.

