### **8.6 Time to Castration Resistance**

Castration resistant prostate cancer is defined as either PSA progression or radiographic progression. Time to Castration resistance will be counted from start of ADT (first LHRH agonist/antagonist/surgical castration) to development of castration resistance by either criterion:

- **PSA progression** per 10.2.1. Castration resistance will be determined to have occurred at the time of the first PSA increase.

- **Radiographic progression** Castration resistance will be determined to have occurred at the time of the first imaging assessment showing progression not the confirmatory scan (for bone lesions).

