### **8.7 Time to Radiographic Progression**

Radiographic progression is defined by imaging (also see notes on PET). For soft tissue lesions, the smallest measurements recorded since the treatment started will be used as reference. For bone scans, the prior scan with least tumor burden scan in bone will be used as reference. Time to radiographic progression will be counted from randomization to radiographic progression.

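### Sections 8.2.2 and 8.7 permit opposite rPFS calls on the same bone scans when new lesions at C8D1 merely persist at C13D1

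*Combined protocol and SAP*

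**What the plan says.** **Counting rules, Section 8.2.2.** Bone progression "is defined as 2 or more new lesions on radionuclide bone scans (PCWG2 criteria". A stricter rule covers two or more new lesions "at the first imaging assessment (at end of protocol specified therapy"): in that case "two or more additional new lesions must be evident on a confirmatory assessment at least 6 weeks later". A separate provision covers new bone lesions without a rising PSA in the first 7 months. The site "must consult the sponsor-investigator (via the HCRN Project Manager) to discuss the possibility of tumor flare", but no rule says how the lesions are counted afterwards.

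**Reference scan, Section 8.7.** "For bone scans, the prior scan with least tumor burden scan in bone will be used as reference". No exception is made for a first scan whose new lesions were not confirmed.

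**Dating.** Section 8.6 dates castration resistance "at the time of the first imaging assessment showing progression not the confirmatory scan (for bone lesions"). Sections 8.7 and 8.8, which define rPFS, contain no matching rule.

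**Schedule, Section 7, footnote 8.** "A bone scan will be performed at baseline, C8D1 and after completion of 1 year of treatment". Section 7.7 places the one-year scan at C13D1. The Cycle 17 visit (Section 7.9) has CT or MRI but no bone scan.

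**Link to the primary analysis.** Section 8.8 builds rPFS on radiographic progression or death, and Section 12.6 sends the primary analysis to Section 8.

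**The concern.** Every subject has bone metastases, measurable soft-tissue disease is not required, and only two post-baseline bone scans are scheduled. How each of those two scans is read therefore matters a good deal to rPFS.

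The stricter rule in 8.2.2 exists so that flare on the first scan is not taken for progression. Section 8.7 can undo that protection. If the reference at C13D1 is the scan with the least bone burden, normally screening, then lesions first seen at C8D1 and unchanged since are still new relative to the reference, and they meet the general threshold.

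Two readers could follow the plan faithfully and disagree on whether an event occurred. Section 5.1 describes no placebo, Section 12.6 speaks of investigator-assessed progression, and I find no central reading of scans. The choice between the two rules may thus be made by people who know the arm. Section 7.10 also takes subjects with radiologic progression off protocol therapy, so a wrong call may not be fully repairable at analysis.

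Two smaller gaps sit beside this one: which scan is the first assessment, and which date a confirmed bone event carries for rPFS.

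**Working it through.** **1. Calendar (28-day cycles, Section 7).** C8D1 = 7 × 28 + 1 = day 197. C13D1 = 12 × 28 + 1 = day 337. The gap is 140 days = 20 weeks = 140/30.4375 = 4.6 months. C13D1 therefore satisfies the 6-week minimum for a confirmatory scan, and it is the last scheduled bone scan.

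**2. One set of scans, two rules.** Take 4 lesions at screening, 7 at C8D1, and the same 7 at C13D1.

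| Rule | Comparison at C13D1 | Count | Call |
|---|---|---|---|
| 8.2.2, confirmation | additional to C8D1 | 7 − 7 = 0 | not confirmed |
| 8.7 reference with the general threshold | new since screening | 7 − 4 = 3 | progression |

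The 8.7 reading is strongest when an unscheduled confirmatory scan between C8D1 and C13D1 was already negative. The confirmation rule has then been used up and no longer clearly covers C13D1.

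**3. Which scan needs confirmation.** Section 3.1 says that protocol specified therapy "refers to the androgen deprivation therapy (see above) with or without radium-223 dichloride", and Sections 7.6 and 7.8 let ADT run up to 2 years from randomization. On that reading C8D1 is not at the end of therapy. Section 5.5.3, footnote 10 of the calendar and the bone-marker schedule in Section 9.1 point to a seven-cycle period, which ends at C8D1. Both readings have support.

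**4. Date of a confirmed event.** If C8D1 lesions are confirmed at C13D1, the rPFS date differs by 140 days according to whether the first or the confirming scan is used. This affects only men with confirmed C8D1 bone progression, and the difference is smaller if an unscheduled scan confirms earlier.

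**5. The plan's own figure.** Inputs from Section 12.1: HR 0.632 (medians 12 and 19 months), 1:2 allocation, one-sided alpha 0.10, power 90%. Schoenfeld: d = (z₀.₉ + z₀.₉)² / [(1/3)(2/3)(ln HR)²] = 6.5695 / (0.2222 × 0.2106) = 140.4, or 140.0 with HR = 12/19. Expected events for 68 + 136 men, with 24 months' accrual, 48 months in total and 10% yearly dropout, are 140.1. The stated 140 reproduces, and this point does not make it wrong.

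**6. Illustration of size.** Assumption: a share f of men, if still event-free and in follow-up at 336/30.4375 = 11.04 months, is falsely called progressed at that time. The expected number at risk then is:
- control: 68 × 0.5^(11.04/12) × 0.9^(11.04/12) ≈ 33
- radium: 136 × 0.5^(11.04/19) × 0.9^(11.04/12) ≈ 83

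So f = 10% means about 3 control men and 8 radium men. The simulation used exponential times and an unstratified log-rank test, with 3,000 trials per cell (Monte Carlo error about 0.5 to 0.8 points).

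| f, control / radium | Power | One-sided type I error |
|---|---|---|
| 0 / 0 | 91.5% | 10.5% |
| 2% / 2% | 90.9% | 10.8% |
| 5% / 5% | 90.0% | 11.0% |
| 10% / 10% | 87.6% | 9.6% |
| 15% / 15% | 86.8% | 10.5% |
| 0 / 5% | 86.8% | 7.9% |
| 0 / 10% | 79.6% | 5.7% |
| 10% / 5% | 92.0% | 14.5% |
| 10% / 0 | 95.3% | 19.0% |

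Further runs with a 10-point radium excess on top of some control flare gave 78-80% power at 5% v 15% and 76-77% at 10% v 20%.

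**The case against.** The strongest reply is that the specific rule governs. Section 8.7 chooses a comparison scan; it sets no lesion threshold and claims no precedence. Section 8.2.2 deals expressly with new lesions at the first assessment and uses mandatory language. With C13D1 read as the confirmatory scan, persistence alone is not progression. One can add that flare foci are arguably not tumor burden, in which case C8D1 need not count as the heavier scan. This stands as a reasonable reading and probably reflects the intent. It is still an inference: no passage states it, and it weakens where a separate confirmatory scan came before C13D1.

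Second, 8.2.2 has another safeguard, the flare consultation. C8D1 falls at 196/30.4375 = 6.4 months, inside its 7-month period. That brings case-level review, but it applies only without a rising PSA and does not say how C13D1 is then counted.

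Third, Section 8 applies PCWG2 to bone lesions, and PCWG2 may itself fix the reference scan. I could not consult it. Section 8.7 nevertheless writes its own reference rule and does not defer to PCWG2.

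Fourth, the size depends on assumed rates. A false call needs two or more flare lesions, persistence to month 11, no additional lesions, and a reader who follows 8.7. That stands: with equal rates of 5% the plan keeps its 90% power, and type I error stays near 10%.

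**Conclusion.** The conflict is real and lies in the event definition of the primary endpoint. Applied as written, 8.2.2 and 8.7 can give event and no event for the same man on the same scans, and nothing ranks them.

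A reader might go further and infer that 8.7 cancels the flare safeguard, so that persisting C8D1 lesions must count as progression. The documents do not support that, because 8.7 does not override the more specific rule; the plan permits the false call and does not mandate it. A reader might also infer a bias against radium, since that arm adds a bone-seeking agent. The documents give no flare rate, no persistence rate and no difference between arms, so the direction is unknown.

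Under the assumed rates, equal false calls of 5-10% leave power at about 90-88%. A 10-point excess in the radium arm cuts it to about 76-80%. A 10-point excess in control only raises one-sided type I error to about 19% against the nominal 10%. The problem is therefore material mainly if false calls differ by arm.

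The end-of-therapy wording is an ambiguity, and the missing rPFS date rule is a drafting gap. Both are secondary, but they belong in the same correction. The passages should be reconciled before rPFS events are called.

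**What to change.** Make three edits in Section 8:

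1. **8.2.2:** replace the end-of-therapy wording with the first post-baseline bone scan (C8D1, or an earlier unscheduled scan) as the one whose new lesions need confirmation.
2. **8.7:** state that if those lesions are not confirmed by two or more additional lesions at least 6 weeks later, that first scan becomes the reference for all later bone scans.
3. **8.8:** date confirmed bone progression at the first scan, as 8.6 already does for castration resistance.

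C13D1 can serve as the confirmatory scan, so no extra imaging is needed. Because Section 7.10 links radiologic progression to leaving protocol therapy, the sponsor should also check that 7.10 and the revised Section 8 agree. I propose no treatment rule.

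The cost is a few sentences of amendment and one statistical downside. No bone scan is scheduled after C13D1, so a few men with true, slow, bone-only progression may be called late, or not called by any scheduled bone scan, once C8D1 is their reference. The amendment should acknowledge this.
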